4.3 Safety Variables

The incidence and type of ocular and non-ocular treatment-emergent adverse events (TEAEs) will be assessed. All adverse events reported by the subject or observed by the investigator at each visit, will be collected from the time the subject signs the ICF until study exit.

Visual acuity (VA) testing will be performed at each visit. Visual acuity will be measured with habitual correction at each visit using a Monoyer chart. The same VA testing method is to be employed for all visits for each subject.

Biomicroscopy assessments will be performed at each visit. Biomicroscopy variables will be evaluated using the grading scales defined in Appendix B.

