Treatment-emergent systemic AEs will be summarized using discrete summary statistics at the subject and event level by system organ class and preferred term for each treatment group. Treatment-emergent ocular AEs will be summarized for treated eyes and fellow eyes separately. Similarly, TEAEs will be summarized by severity and relationship separately.

Categorical endpoints will be analyzed using Fisher's exact test or chi-square test where it is appropriate.

All the statistical tests will be performed at significance level $\alpha=0.05$.

The details of the analysis will be documented in the Statistical Analysis Plan (SAP) which will be reviewed at the masked data review and finalized before breaking the treatment codes.

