APPENDIX A: SCHEDULE OF VISITS AND PARAMETERS

All study tasks should be performed by qualified study site personnel as indicated on the delegation of authority log under the supervision of the Principal Investigator. Furthermore, all ocular signs must be evaluated by an ophthalmologist.

PROCEDURE/ASSESSMENTS	Visit 1	Visit 2	Visit 3	Visit 4	Visit 5
	Screening	Inclusion	Follow-up Telephone call ^d	Follow-up	Study Exit
	ART run in	Baseline			
	Day -14 (up to -16 days)	Day 0	Day 7 (± 1 day)	Day 28 (± 3 days)	Day 90 (± 10 days)
Informed Consent	X				
Demographic data	X				
Current and relevant medical and ocular history	X				
Pregnancy test, if applicable	X				
Concomitant medication	X	X	X	X	X
Dry eye symptoms	X	X		X	X
OSD-QoL® questionnaire		X			X
Visual acuity	X	X	X ^e	X	X
Biomicroscopy	X	X	X ^e	X	X
TFBUT	X	X		X	X
Fluorescein staining	X	X		X	X
Schirmer test		X		X	
Eligibility determination	X	X			
Randomization		X			
Dispense run-in ART	X				

Version 3, 25 Jul 2017

A-1

Study #CBL-2017-01- Protocol

PROCEDURE/ASSESSMENTS	Visit 1	Visit 2	Visit 3	Visit 4	Visit 5
	Screening	Inclusion	Follow-up Telephone call ^d	Follow-up	Study Exit
	ART run in	Baseline			
	Day -14 (up to -16 days)	Day 0	Day 7 (\pm 1 day)	Day 28 (\pm 3 days)	Day 90 (\pm 10 days)
Collect run-in ART		X			
Dispense diary ^a	X	X		X	
Collect diary ^b		X		X	X
Dispense investigational eye drops		X		X	
Collect investigational eye drops in a sealed container					X
Review subject diary for compliance		X	X ^e	X	X
Adverse events ^c	X	X	X	X	X
Exit subject					X

Abbreviations: ART = artificial tears; OSD-QoL = Ocular Surface Disease-Quality of Life; TFBUT = tear film break-up time

^a Diary A will be dispensed at Visit 1, Diary B will be dispensed at Visit 2, and Diary C will be dispensed at Visit 4

^b Diary A will be collected at Visit 2, Diary B will be collected at Visit 4, and Diary C will be collected at Visit 5

^c Adverse events will be collected from the time the subject signs the ICF to study exit

^d Telephone call assessment for compliance and collection of adverse events by the Investigator or designee. The Investigator should determine whether subject should come for a visit or not

^e If visit performed

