## 3 STUDY OVERVIEW

### 3.1 Objectives

The primary objectives of this investigation are to show that the performance of CBL-102 Eye Drops is non-inferior to that of Vismed® Multi eye drops in subjects with moderate to severe keratoconjunctivitis sicca after 28 days, and to assess the safety of CBL-102 Eye Drops during a 90-day period with treatment administered 3 to 6 times per day.

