### 3.4.3 Safety Endpoints

The safety endpoints include the following:

- Occurrence rates of ocular and non-ocular TEAEs.
- Visual Acuity measured with habitual correction, using Monoyer chart.

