### 7.7.1 Bio-microscopic examination

Each sign will be described by treatment group and by eye (Studied eye and fellow eye) at each visit with an available data at the given visit. The worst grade observed during the study (Studied eye and fellow eye combined) will also be described by treatment group.

Data at the follow-up visits will be cross-tabulated with the data at baseline D0 and will be described in 6 classes: No change (no sign) / Disappearance / Improvement / No change (persistence of the sign) / Aggravation / Onset. If necessary, modalities will be pooled depending on the number of subjects.

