### 7.7.4 Adverse events

All adverse events variables, as described in the §3 “Safety variables” will be described and compared between groups (chi-square test or a Fisher exact test depending on the sample size).

All adverse events will be described in each treatment group by MedDRA’s « System Organ » and « Preferred Term ».

All adverse events will also be listed by group.

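### The SAP's by-term adverse event table pools run-in events with treatment-emergent ones, and the protocol's severity and eye-level TEAE summaries are missing from the SAP without being declared

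*SAP*

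**What the plan says.** Safety is one of the two primary objectives: "to assess the safety of CBL-102 Eye Drops during a 90-day period with treatment administered 3 to 6 times per day" (SAP 3.1). The first named safety endpoint is "Occurrence rates of ocular and non-ocular TEAEs" (SAP 3.4.3); the other is visual acuity.

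Protocol 4.3 states that adverse events "will be collected from the time the subject signs the ICF until study exit", and Appendix A repeats it. Collection therefore covers the artificial-tear run-in before randomisation.

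Protocol 7.6.1 sets out the tables: "Treatment-emergent systemic AEs will be summarized using discrete summary statistics at the subject and event level by system organ class and preferred term" for each arm, ocular TEAEs separately for treated and fellow eyes, and, in the same way, "TEAEs will be summarized by severity and relationship separately".

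SAP 7.7.4 says instead: "All adverse events will be described in each treatment group by" MedDRA system organ class and preferred term. The shell in SAP 7.13.4 counts patients who had the term at least once. It has no treatment-emergent restriction, event count, severity column or relationship column. SAP 7.4 adds a separate by-term table of events before investigational treatment.

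For biomicroscopy, SAP 7.7.1 adds to its by-visit and shift tables a by-arm summary of "The worst grade observed during the study (Studied eye and fellow eye combined"). SAP 6.3 gives the evaluation times for these signs as D0, D28 and D90.

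SAP section 4, which lists departures from the protocol's statistical section, mentions none of these differences.

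**The concern.** A by-term table headed by the randomised products is where a reader looks to see what each product did. Here it would contain events that began on the povidone run-in drops, before either product was used. Run-in events should be balanced between arms in expectation, so they add noise and shrink ratios between arms rather than favour one product.

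Severity is assessed for every event (Protocol 6.8) and imputed when missing (SAP 7.12), yet it enters no SAP variable or table. The planned summaries would not say whether the treatment-emergent events in each arm were mild or severe, although the protocol promised that. Because section 4 is silent, a reader of the report could not tell whether the reduction was intended.

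**Working it through.** The plan gives no figure on this point, so the check is mainly a comparison of texts.

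**1. Protocol 7.6.1 against the SAP**

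| Protocol 7.6.1 | SAP | Status |
|---|---|---|
| Systemic TEAEs by organ class and term, subject and event level | All AEs by organ class and term, subject level (7.7.4, 7.13.4) | Changed |
| Ocular TEAEs by treated and fellow eye | None | Absent |
| TEAEs by severity | Imputation rule only (7.12) | Absent |
| TEAEs by relationship | Yes/no flags for ocular and non-ocular TEAEs related to the drops, and to the procedure (6.3) | Reduced |

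SAP 6.3 lists AEs and TEAEs as separate variables and defines the latter, so the wording in 7.7.4 cannot be read as shorthand for TEAEs.

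**2. Can TEAEs by term be recovered by subtraction?** Assume the SAP 7.4 table uses the same shell, the only adverse event shell given. For one term in one arm, let a = subjects with it in the run-in only, b = on treatment only, c = in both periods.

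- All-AE table: a + b + c
- Pre-treatment table: a + c
- Difference: (a + b + c) − (a + c) = b
- Subjects with the term as a TEAE: b + c

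The difference misses c. An event that starts in the run-in and worsens on treatment is a TEAE under the SAP's definition, but it is in the pre-treatment table and would also be subtracted.

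**3. Length of the pre-treatment window.** Run-in is 14 to 16 days and treatment 90 ± 10 days (Protocol 2.4). Share = run-in / (run-in + treatment).

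- Nominal: 14 / (14 + 90) = 13.5%
- Lowest: 14 / (14 + 100) = 12.3%
- Highest: 16 / (16 + 80) = 16.7%

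This is a share of time, not of events or subjects.

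**4. Illustration of dilution, on assumed rates.** Take a TEAE risk of 20% against 10% and an independent run-in risk p0 of 3% to 10%, equal in both arms. The all-AE risk is 1 − (1 − p0)(1 − TEAE risk).

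- p0 = 3%: 22.4% against 12.7%; difference 9.7 points, ratio 1.76
- p0 = 10%: 28.0% against 19.0%; difference 9.0 points, ratio 1.47
- TEAEs only: difference 10.0 points, ratio 2.00

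The difference barely moves; the ratio moves more.

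**5. Worst grade.** With D0 among the evaluation times, a subject graded 2 at D0 and 1 at both later visits has a worst grade of 2. The summary then reports a pre-treatment finding and hides the improvement.

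**The case against.** The strongest reply is that the SAP keeps what the endpoint needs. SAP 6.3 defines subject-level flags for any, ocular, non-ocular and serious TEAEs, and 7.7.4 describes and compares them by arm. Visual acuity is summarised at D28 and D90 and as change from baseline. Device deficiencies are split at D0, pre-treatment events have their own table, and biomicroscopy is shown by visit and eye with a six-class shift from D0 that isolates onset and worsening. All of this stands. A reader might infer that the arm-level safety tables in general mix periods, or that the safety objective cannot be met; the documents support neither.

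A reader might also infer that relationship has been dropped. It has been reduced: the related-TEAE flags remain, while the individual causality categories and any by-term view are lost. The adverse device effect flags do not fill that gap, because SAP 6.3 detects such effects only through a reported device deficiency.

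It can be said that the by-term table is only described, not tested, and that all events are listed by group. Both are true, but a listing is not a summary, and the flags count subjects without naming events.

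Finally, since section 4 declares no change, the protocol's tables could be taken as still standing. But SAP section 2 makes the analyses it outlines the basis of the final report, and Protocol 7.6.1 leaves the detail to the SAP. The ambiguity is itself a reason to settle the wording.

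The biomicroscopy point is the weakest part: the worst grade is an extra descriptive line on a variable that is not a named safety endpoint.

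**Conclusion.** The point holds as a loss of by-term and severity detail on a primary objective. SAP 7.7.4 and shell 7.13.4 pool run-in and treatment-emergent events under each arm, contrary to Protocol 7.6.1, and no other planned table shows treatment-emergent events by term. The severity summary and the ocular eye split are absent, relationship is reduced to yes/no counts, and none of this is declared in SAP section 4. The worst biomicroscopy grade can, as worded, include D0; that rests on reading the SAP 6.3 evaluation times into 7.7.1.

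Occurrence of ocular and non-ocular TEAEs and visual acuity remain analysable as planned.

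The run-in is 12% to 17% of the collection window. It is tempting to conclude that about one event in seven or eight in the table would precede treatment. That needs a constant event rate, which the documents do not support, and the table counts subjects rather than events. The share affected is unknown, and the dilution figures above rest wholly on assumed risks. The change should be made, but it is a correction to reporting, not a threat to the trial's main conclusion.

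**What to change.** - In SAP 7.7.4 and 7.13.4, restrict the organ class and preferred term tables to TEAEs, ocular and non-ocular separately, with subject and event counts.
- Present ocular TEAEs by study eye and fellow eye. The protocol's term treated eye needs this reading, because both eyes receive the drops (Protocol 2.5).
- Add TEAE tables by severity and by relationship category, as Protocol 7.6.1 specifies. The severity imputation rule in SAP 7.12 then has an output to feed.
- Keep pre-treatment events in the SAP 7.4 table.
- In SAP 7.7.1, define the worst biomicroscopy grade over post-baseline visits.
- Correct the cross-reference in 7.7.4, which points to section 3 although the safety variables are in 6.3.
- Declare in SAP section 4 any protocol table that is deliberately left out.

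The cost is SAP wording and a few extra tables. The onset, severity and causality data are already collected, and neither the sample size nor the primary performance analysis is affected.

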## 7.8 Tolerability and ease-of-use

These analyses will be performed on the Safety population. Results of statistical tests will be two-sided and given for information purpose only.

Each variable will be described by group at each evaluation time. Both groups will be compared at D90 by a chi-square test or a Fisher exact test depending on the sample size.

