### 6.3 Safety Variables

Topic	Area	Analyzed parameters	Time of evaluation
Bio-microscopic examination	Each eye	
 
- Eyelid Erythema
 
- Eyelid Swelling
 
- Ocular Discharge
 
- Conjunctival Chemosis
 
- Conjunctival Hyperemia
 
- Corneal Erosion
 
- Corneal Edema
 
- Corneal Infiltrates
 
	D0 / D28 / D90
Visual acuity test	Each eye	
 
- LogMAR = -Log(Visual acuity decimal)
 
	D0 / D28 / D90
Adverse events	All body	
 
- At least one AE during the study
 
- At least one TEAE during the study
 
- At least one ADE during the study
 
- At least one serious AE during the study
 
- At least one serious TEAE during the study
 
- At least one serious ADE during the study
 
- At least one unanticipated serious ADE during the study
 
- At least one anticipated serious ADE during the study
 
	During all study
Adverse events	Ocular	
 
- At least one ocular AE during the study
 
- At least one ocular TEAE during the study
 
- At least one ocular ADE during the study
 
- At least one ocular TEAE related (possible, probable, certain) to the eye drops during the study
 
- At least one ocular TEAE related (possible, probable, certain) to the procedure during the study
 
- At least one serious ocular AE during the study
 
- At least one serious ocular TEAE during the study
 
- At least one serious ocular ADE during the study
 
- At least one unanticipated serious ocular ADE during the study
 
- At least one anticipated serious ocular ADE during the study
 
- Ocular AE description
 
	During all study

Topic	Area	Analyzed parameters	Time of evaluation

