## 6.6 Tolerability and ease-of-use

Analyzed parameters	Description	Time of evaluation
Upon instillation, these eye drops are comfortable in my eyes	Strongly agree / agree / disagree / Strongly disagree	Diary D7 / D28 / D56 / End of last week or day before D90
The bottle is easy to use	Strongly agree / agree / disagree / Strongly disagree	Diary D28 / End of last week or day before D90
I can instill exactly one drop with this bottle	Strongly agree / agree / disagree / Strongly disagree	Diary D28 / End of last week or day before D90

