## 7.6 Secondary performance endpoint analyses

All secondary performance endpoint analyses will be performed on the ITT and PP populations. Results of statistical tests will be two-sided and given for information purpose only.

The secondary performance variables will be described by treatment group at each visit on raw values and on the changes / baseline D0.

The treatment groups will be compared at each post-baseline time using the same covariance model used to analyze the primary endpoint. The interaction Treatment x Baseline will be tested and removed from the model if not significant. If significant, the interaction will be kept in the model (a graphical representation of the interaction will be displayed) and the Treatment effect will be approximated by using the global average of observed D0 values (Note that in case of interaction, the Treatment effect cannot be properly interpreted). In addition, the distribution of the residuals of the analysis of variance will be tested: if the normality is not verified (Shapiro-Wilk test at the 1% threshold), the analysis will be performed on the ranks of the data (if analyses on ranks and on raw values lead to the same conclusions, only analysis on raw values will be given).

Depending on the distribution of the data (multinomial data such as global assessment of dry symptoms evaluations), a sensitivity analysis will be performed to compare both groups using a generalized linear model for multinomial data (SAS® Glimmix Procedure) with the value at baseline as covariate.

For the Ocular surface fluorescein staining test, the % of patients with a total score at 0 at D28 and D90 will be given with its 95% confidence interval.

Graphical representations by bar charts will be provided for dry eye symptoms and OSD-QoL dimension scores.

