### 7.7.2 Visual acuity

The visual acuity (decimal value) will be described for each eye (Studied eye and fellow eye) by treatment group at D28 and D90 by class:  $\geq 8/10$ ,  $<8/10$  and  $\geq 5/10$ ,  $< 5/10$  and  $\geq 1/10$ ,  $< 1/10$ .

Visual acuity decimal values will also be transformed into LogMar values for summary statistics at each time and on changes / baseline. They will be compared between the 2 groups at D28 and D90 (Student t-test for independent samples or a Wilcoxon rank-sum test if the data do not follow a normal distribution).

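### SAP 7.7.2 compares LogMAR without a baseline covariate and does not say whether values or changes are tested; SAP 7.8 compares ordered diary items with tests that ignore order

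*SAP*

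**What the plan says.** **Visual acuity.** SAP 6.3 defines the variable for each eye as the negative log of decimal acuity, evaluated at D0, D28 and D90. Protocol 5.1.2 and Appendix A also schedule the measurement at Visit 2, so a baseline exists. Under Visual acuity, SAP 7.7.2 first states: "Visual acuity decimal values will also be transformed into LogMar values for summary statistics at each time and on changes / baseline". The next sentence gives the test: "They will be compared between the 2 groups at D28 and D90 (Student t-test for independent samples or a Wilcoxon rank-sum test", with Wilcoxon used when the data are not normal. No covariate is named.

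**Practice elsewhere in the SAP.** SAP 7.6 compares secondary performance endpoints with the baseline-adjusted covariance model of the primary analysis. It adds a rank fallback: "if the normality is not verified (Shapiro-Wilk test at the 1% threshold), the analysis will be performed on the ranks of the data". Neither is extended to 7.7.2.

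**Diary items.** SAP 6.6 lists comfort on instillation and two bottle items, each answered "Strongly agree / agree / disagree / Strongly disagree". SAP 7.8 describes them by group at each time and tests them at D90: "Both groups will be compared at D90 by a chi-square test or a Fisher exact test depending on the sample size". The same section adds: "Results of statistical tests will be two-sided and given for information purpose only". The test choice follows Protocol 7.6.1: "Categorical endpoints will be analyzed using Fisher's exact test or chi-square test where it is appropriate".

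**The concern.** In 7.7.2 the pronoun that opens the comparison sentence follows a sentence naming both the values at each time and the changes from baseline. Two programmers could each follow the text, test different quantities, and report different estimates, intervals and p-values for a safety endpoint. Whichever quantity was meant, no baseline covariate is used, although the measurement is in hand and the SAP adjusts for baseline elsewhere. The label that makes tests informational appears in 7.8 but is not repeated in 7.7.2.

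In 7.8 the four responses run from best to worst. Pearson chi-square and the standard Fisher exact test give the same p-value if the four columns are shuffled. They spread their sensitivity over every kind of difference, including those in which neither product is rated better overall.

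What is at stake is clarity and precision for secondary and safety comparisons. Validity is not in question.

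**Working it through.** **The plan's own figure.** The documents give no power or precision figure for these comparisons. Their sample size, for the primary staining endpoint, reproduces:
- n per arm = 2 × (1.960 + 1.282)² × 2.5² / 2² = 32.8, so 33.
- 33 / 0.80 = 41.25, so 42 per arm and 84 in total.

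The check on the diary items uses 42 per arm (all randomized) and 38 per arm (84 × 0.9 / 2 = 37.8).

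**LogMAR.** Assume equal variance at baseline and follow-up and a correlation ρ between them. The documents give no ρ, so 0.5 to 0.9 is a range of assumptions. Relative to a test of raw values (SE = 1):
- test of changes: SE = √(2(1 − ρ))
- ANCOVA: SE = √(1 − ρ²)
- ANCOVA relative to changes: √((1 + ρ)/2)

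| ρ | SE, changes | SE, ANCOVA | ANCOVA cut vs raw values | ANCOVA cut vs changes |
|---|---|---|---|---|
| 0.5 | 1.00 | 0.87 | 13% | 13% |
| 0.7 | 0.77 | 0.71 | 29% | 8% |
| 0.8 | 0.63 | 0.60 | 40% | 5% |
| 0.9 | 0.45 | 0.44 | 56% | 3% |

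The two readings of 7.7.2 have the same precision at ρ = 0.5. At ρ = 0.7 to 0.9, raw values have 1/0.60 = 1.7 to 1/0.20 = 5 times the variance of changes.

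Simulated bivariate-normal trials (ρ 0.7 to 0.9, 38 and 42 per arm) used an effect set for 80% nominal ANCOVA power. Power was 78–79% for ANCOVA, 72–78% for a t-test of changes and 23–51% for a t-test of raw values. Null rejection was 4.5–5.5% for all three. The Wilcoxon branch of 7.7.2 was not simulated.

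**Diary items.** All response shares are assumed. Chi-square and Fisher are shown separately because 7.8 gives no rule for switching between them. Figures are simulated power at two-sided 0.05.

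| Assumed shares (%) | Per arm | Chi-square | Fisher | Rank-sum |
|---|---|---|---|---|
| 50/40/8/2 vs 25/45/22/8 | 38 | 60% | 62% | 77% |
| same | 42 | 66% | 68% | 82% |
| 45/40/10/5 vs 25/40/20/15 | 38 | 47% | 47% | 64% |
| same | 42 | 51% | 51% | 68% |

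The rank-sum gain is 16–18 points over chi-square and 14–17 over Fisher. These are large shifts, with cumulative odds ratios of about 3.0–4.3 in the first scenario and 2.5–3.4 in the second. For smaller shifts from the same reference shares, at 38–42 per arm:
- Odds ratio 2: chi-square 21–25%, Fisher 24–29%, rank-sum 35–40%.
- Odds ratio 1.5: chi-square 9–11%, rank-sum 15–17%.

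Null rejection is 3–5% for all three tests. In the opposite case, a difference in spread without a shift (40/40/15/5 vs 55/15/15/15), rank-sum power is about 7%, against roughly 62–66% for chi-square or Fisher.

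**The case against.** The strongest reply on visual acuity is that the baseline may already be used. If changes are tested, D0 enters by subtraction, and 7.7.2 names changes in the sentence just before the test. A reader might infer that the plan discards the baseline. The text does not support that: only the absence of a baseline covariate is certain. If changes were meant, one clarifying word would cure most of the problem, since ANCOVA then adds only 3–13%. This stands, and it limits the size of the point. The ambiguity remains, and ANCOVA is at least as precise under either reading.

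On the diary items, the reply is that chi-square and Fisher are valid, follow the protocol, and are labelled informational. Nothing in the documents names an ordered shift as the contrast of interest, the large gains rest on large assumed shifts, and a rank test has a blind spot of its own. All of this stands. The ordered test is a trade-off that suits the usual question of which product is rated better. It does not correct an error.

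A further fair objection is that the rank rule in 7.6 should not be imported wholesale. It shows only the raw-value result when the two analyses agree, and it sits beside a pretested treatment-by-baseline interaction. The fallback therefore has to be named.

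**Conclusion.** The point holds as an inexpensive improvement. For LogMAR, 7.7.2 leaves the tested quantity undefined and uses no baseline covariate. With an assumed correlation of 0.5 to 0.9, ANCOVA reduces the standard error by 13–56% against raw values and by 3–13% against changes, so the gain is small if changes were intended. The formulas assume equal variances, and the simulated power assumes normal data.

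For the diary items, the order is ignored in tests that are informational only. The gain of about 14–18 points applies to large assumed shifts. At an odds ratio of 2 or below, no test is sensitive at this sample size.

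A reader might infer that these tests are invalid or weaken the trial's main claim. They do neither. Each planned test is valid under randomization, simulated null rejection does not exceed its nominal level materially, and the non-inferiority analysis and sample size concern only the staining score.

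**What to change.** **SAP 7.7.2.** Compare LogMAR at D28 and D90, study eye and fellow eye separately, by ANCOVA with treatment and baseline LogMAR. Name one fallback for non-normal residuals, for example ANCOVA on the ranks of follow-up and baseline LogMAR, and say which result is reported. Do not carry over the pretested treatment-by-baseline interaction of 7.6. If ANCOVA is not adopted, at least state whether values or changes are tested.

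**SAP 7.8.** Use a Wilcoxon rank-sum (row-mean-score) test at D90 for the three items. Keep the category tables already planned, which would still show a difference in spread, and leave the other time points descriptive.

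**SAP section 4.** List both changes, since Protocol 7.6.1 names Fisher or chi-square for categorical endpoints. Make them before the treatment codes are broken.

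The cost is a few lines of text and minor programming. No new data are needed and no tests are added: LogMAR stays at two times for each eye, and the diary items stay at three tests. The one loss is the rank test's insensitivity to a difference in spread.

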2.2.3 Subject Discontinuation

A subject MAY be discontinued (at the discretion of the Investigator, the Sponsor, and/or the EC) prior to the final visit for several reasons, including, but not limited to:

- A serious adverse event (SAE) occurring during the course of the study, which precludes continued treatment or follow-up
- The subject not following required study procedures
- If a subject exhibits intolerable AEs (related or not related to the investigational medical device), or if a subject fails to show improvement or the clinical status worsens, the treating Investigator may opt to withdraw the subject from the study and implement necessary intervention.

A subject MUST be discontinued prior to the final visit for any of the following reasons:

- Voluntary withdrawal
- Death
- Investigator decision that it is not in the best medical interest of the subject to continue participation in the investigation. In case a subject administers more than 8 instillations per day for both eyes on a regularly continued basis (approximately 70 %) as assessed on Visit 4, the subject will be discontinued from the study and the investigator will prescribe an appropriate treatment.

Prior to discontinuing a subject, every effort should be made to contact the subject, schedule a final visit, obtain as much follow-up data as possible, and to retrieve all investigational materials. Adverse events will be followed as described in Section 6.5 . Subject withdrawals will be documented clearly on the source document and applicable electronic case report form (eCRF). The assessments scheduled for Visit 5 should be performed at this early termination visit.

Notification of subject discontinuation will be made to the Sponsor Representative and will be clearly documented on the applicable eCRF. Any subject discontinued from the study will not be replaced.

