7. SUBJECT DIARY

The subject will be asked to fill in a diary.

- a. **Diary Card A for Run-In ART (Visit 1):** This diary will be provided to each subject on the day of Visit 1 (Screening, Day -14) and will be used for 2 weeks until Visit 2 (Day 0, baseline).

This diary will capture the frequency per day of run-in ART instillations.

- b. **Diary Card B and C for Investigational Eye Drops (Visits 2-5):** Diary Card B will be provided to each subject at Visit 2 (Baseline) and will be used through Visit 4 (Day 28 ± 3 days). Diary Card C will be provided to each subject at Visit 4 (Day 28 ± 3 days) and will be used through Visit 5 (Day 90 ± 10 days).

This diary will capture the following information:

[figure not shown]
[figure not shown]
[figure not shown]
[figure not shown]
[figure not shown]
- Daily: frequency per day of investigational eye drop instillations
- At the end of the first week and then at the end of each month: investigational eye drop tolerability just after the first instillation of the day. The subject will be asked to provide information on:
 - Investigational eye drop sensation : “upon instillation these eye drops are comfortable in my eyes” (strongly agree/agree/disagree/strongly disagree)
- At the end of Diary Cards B and C: ease-of-use. The subject will be asked to grade the following sentences:

Study #CBL-2017-01- Protocol

- “The bottle is easy to use” (strongly agree/agree/disagree/strongly disagree)
- “With this bottle I can dispense exactly one drop” (strongly agree/agree/disagree/strongly disagree)

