## 7.12 Missing data

For subjects who discontinued the study early, analyses of change from baseline to endpoint for continuous variables will be based on the last non-missing post-baseline data (last observation carried forward data imputation methodology).

For safety data, if the causality assessment of an AE is missing, it will be imputed as “Probably” related to the investigational treatment. Likewise, if the severity is missing, the AE will be assessed as “Severe”.

Regarding diaries, missing data will be discussed during the masked review.

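### Comfort on instillation is tested between arms only at D90, with no rule for counting subjects who stopped earlier, so discomfort-driven loss can shrink a difference

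*SAP*

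**What the plan says.** The SAP's list of tolerability variables (6.6) gives the comfort rating four times: "Diary D7 / D28 / D56 / End of last week or day before D90". The protocol's diary instructions (Appendix B, item 7) agree: "At the end of the first week and then at the end of each month: investigational eye drop tolerability". The answer is one of four ordered categories, from strongly agree to strongly disagree, and there is no baseline value.

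SAP 7.8 handles the rating in four statements:

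- Population: "These analyses will be performed on the Safety population".
- Description: "Each variable will be described by group at each evaluation time".
- Test: "Both groups will be compared at D90 by a chi-square test or a Fisher exact test depending on the sample size".
- Status: "Results of statistical tests will be two-sided and given for information purpose only".

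The restriction of the test to D90 comes from the SAP. Protocol 7.6.1 says only that categorical endpoints are analyzed by Fisher's exact or the chi-square test, and names no time. SAP section 4, which lists changes from the protocol's statistical section, gives no reason for choosing D90.

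On missing values, SAP 7.12 carries the last observation forward, but its scope is limited: "analyses of change from baseline to endpoint for continuous variables will be based on the last non-missing post-baseline data". Missing diary data are left to the masked review.

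**The concern.** Poor comfort is one reason to stop using an eye drop, and the protocol foresees withdrawal on such grounds (2.2.3): "If a subject exhibits intolerable AEs (related or not related to the investigational medical device", after which the investigator may withdraw the subject. Whether a subject is still rated at D90 can therefore depend on the outcome being measured.

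The population label does not cure this. The Safety population includes everyone who received a dose, but the D90 test can use only those with a rating assigned to D90. If one product is less comfortable and more of its users stop for that reason, the subjects left for the test are those who found it acceptable. The single tolerability p-value in the report would then understate the difference. Choosing between chi-square and Fisher does not help, because the problem lies in who is rated at that time.

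**Working it through.** **Does any rule bring early leavers into the D90 test?**

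1. Carry-forward (SAP 7.12) applies to change from baseline in continuous variables. Comfort is categorical and has no baseline, so it is not covered.
2. The treatment exposure and compliance rows of SAP 6.5 run to D90 or the end of study. The comfort row of SAP 6.6 mentions only the last week or the day before D90.
3. Protocol 2.2.3 asks for the Visit 5 assessments at early termination, and Visit 5 includes collecting the diary. A last rating may therefore exist, but nothing assigns it to D90.
4. The masked review will discuss missing diary data, but no rule is written in advance.

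**Arm size.** The plan's own figure reproduces with the usual formula:

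- n = 2 × (1.960 + 1.282)² × 2.5² / 2² = 32.8, so 33 per arm.
- With 10% dropout and 10% violations, 33 / (1 − 0.20) = 41.25, so 42 per arm and 84 in total.

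This size is for the primary endpoint. The documents give no power for tolerability and no expected discomfort rate, so every rate below is an assumption. Uncomfortable means disagree or strongly disagree, and ratings of those who remain are taken as unchanged over time.

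**Illustration A.**

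- D7: 10/42 (23.8%) against 2/42 (4.8%), a difference of 19.0 points; Fisher p = 0.026.
- Of these, 7 and 1 stop. Dropout is 8/84 = 9.5%, within the planned 10%.
- D90: 3/35 (8.6%) against 1/41 (2.4%), a difference of 6.1 points; p = 0.33.

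**Illustration B, smaller numbers.** Four uncomfortable subjects stop in one arm and none in the other.

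- D7: 6/42 (14.3%) against 2/42 (4.8%), a difference of 9.5 points; p = 0.26.
- D90: 2/38 (5.3%) against 2/42 (4.8%), a difference of 0.5 points; p = 1.0.

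Neither test is significant. What changes is the estimate.

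**Range.** Let p be the D7 discomfort rate and f the fraction of uncomfortable subjects who have stopped by D90. The rate among those still rated is p(1 − f) / (1 − pf). For example, p = 0.25 and f = 0.5 give 0.125 / 0.875 = 14.3%. Power is exact, for the two-sided Fisher test at 0.05.

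| D7 rates | f | Total dropout | Difference seen | Power |
|---|---|---|---|---|
| 25% vs 5% | 0 (D7) | – | 20.0 points | 68% |
| | 0.25 | 3.8% | 16.2 | 59% |
| | 0.50 | 7.5% | 11.7 | 47% |
| | 0.75 | 11.2% | 6.4 | 17% |
| 30% vs 10% | 0 (D7) | – | 20.0 points | 56% |
| | 0.25 | 5.0% | 16.6 | 51% |
| | 0.50 | 10.0% | 12.4 | 37% |
| | 0.75 | 15.0% | 7.0 | 17% |

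The two rows with f = 0.75 exceed the planned 10% dropout. The others are within it.

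**The case against.** The strongest reply is that nothing is hidden. The sentence just before the test has every variable described by group at each time, so 10/42 against 2/42 at D7 would appear in the planned tables, and only its p-value would be missing. That p-value is for information, and no tolerability claim rests on it. Withdrawal for intolerance is also partly captured elsewhere: adverse events are compared between groups over the whole study (SAP 6.3 and 7.7.4), and discontinuations with reasons are listed by group (SAP 7.3). D90 matches the 90-day safety objective. All of this stands, and it keeps the point small. It does not supply a rule for early leavers, and a diary answer of disagree need not be reported as an adverse event.

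The illustrations can also be criticized. They attribute every loss to discomfort, although the planned 10% covers dropout for any cause, and illustration B gives the comparator no losses. They show what planned dropout could do and are not forecasts.

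Four stronger readings are tempting, and the documents do not support them:

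- A reader might infer that an early difference would go unseen. The descriptive tables exclude that.
- A reader might infer that nearly everyone will have a D7 rating. No diary completion rate is given. The rating sits in Diary B, collected at Visit 4, and Visit 3 is by default a telephone call. A subject who stops in week 1 or never returns Diary B is missing at D7 too.
- A reader might infer that subjects who stop have no late rating at all. One may be collected at the early termination visit. What is missing is a rule for using it.
- A reader might extend the point to the two bottle questions. Nothing here shows that their D90 comparison is affected in the same way.

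**Conclusion.** The point holds as a low-cost improvement to one informational analysis. The only between-arm test of comfort is placed at the scheduled time most exposed to loss caused by discomfort, and the SAP does not say how early leavers count. Under the assumed rates, and with total dropout at or below the planned 10%, a 20-point D7 difference falls to between about 12 and 17 points at D90. Power falls from 68% to between 47% and 59%, or from 56% to between 37% and 51%. More concentrated stopping gives larger losses, as illustration A shows.

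This rests on discomfort leading to stopping, on more such stopping in one arm, and on stable ratings among those who stay. If discomfort does not drive dropout, the D90 test is little affected. The primary non-inferiority conclusion is not touched.

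**What to change.** Amend SAP 7.8 before unmasking. Protocol 7.6.1 allows this, since the SAP is finalized after the masked review and before the codes are broken.

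- Compare comfort between arms also at D7, in all Safety-population subjects with a rating.
- Compare each subject's worst rating over all diary entries (or the last available rating; choose one in advance), so that early leavers with any rating are counted.
- Report the number rated per arm at each time.
- Label the D90 comparison as applying to subjects still on treatment.

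The diaries already collect the data, so the cost is a few sentences and a few tables. The downsides are a few more informational p-values and, for the worst rating, more opportunities for a poor answer among subjects who stay longer. Subjects who stop in week 1 or do not return Diary B may still be missing, which is why the numbers rated should be shown.
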